4.1.4 Subject Enrollment and Randomisation

Study participation begins (ie, a subject is “enrolled”) once written informed consent is obtained. Once informed consent is obtained, a subject identification (SID) number will be assigned by a central system (eg, an interactive voice/web response system [IXRS]), and the screening evaluations may begin to assess study eligibility (inclusion/exclusion) criteria. The SID number will be used to identify the subject during the screening process and throughout study participation, if applicable.

A master log of all consented subjects will be maintained at the site and will document all screening failures (ie, subjects who are consented but do not meet study eligibility criteria and/or are not randomised), including the reason(s) for screening failure.

Subjects who fail to meet the eligibility criteria should not, under any circumstances, be enrolled or receive investigational product. There can be no exceptions to this rule. Subjects who are enrolled, but subsequently found not to meet all the eligibility criteria must not be randomised or initiated on treatment, and must be withdrawn from the study.

Subjects may be rescreened once if, in the opinion of the investigator, there is a reason to believe they may be eligible.

4.1.5 Withdrawal from the Study

Subjects are at any time free to withdraw from the study (investigational product and assessments), without prejudice to future treatment (withdrawal of consent). At the time of withdrawing consent, subjects will be asked about the reason(s) for withdrawing and the presence of any AEs. After consent is withdrawn, no further study visits or data collection should take place.

4.1.6 Discontinuation of Investigational Product

An individual subject will not receive any further investigational product if any of the following occur in the subject in question:

- Withdrawal of consent from further treatment with investigational product or lost to follow-up
- An AE that, in the opinion of the investigator or the sponsor, contraindicates further dosing
- Subject is determined to have met one or more of the exclusion criteria or failed to meet all of the inclusion criteria for study participation at study entry and continuing investigational product, in the decision of the investigator, might constitute a safety risk
- Subject noncompliance that, in the opinion of the investigator or sponsor, warrants withdrawal (eg, refusal to adhere to scheduled visits).
- Pregnancy in a female subject

Subjects who are permanently discontinued from receiving investigational product will be followed for protocol-specified assessments including follow-up of any AEs unless consent is withdrawn specifically from further study participation (Section 4.1.5), the subject is lost to follow-up, the subject starts alternative treatment, or the subject is enrolled in another clinical study.

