4.7.2 Prohibited Concomitant Medications

Other than the medications described above, use of concomitant medications including over-the-counter medications, herbal supplements, vitamin, etc at the times specified in the list below is not permitted. Subjects must be instructed not to take any medications, including over-the-counter products, without first consulting with the investigator.

Subjects should not be initiated on any new medications to control blood glucose levels during the dosing and follow-up period unless it is deemed necessary by the investigator for safety and following discussion with the medical monitor. Refer to Section 3.1.4.3 for further details.

- Concurrent or previous use of a GLP-1 analogue containing preparation within the last 30 days or 5 half-lives of the drug, whichever is longest, prior to the start of screening (Visit 1)
- Concurrent use of any herbal preparations or medicinal products licensed for control of body weight or appetite and within 1 week prior to the start of the study (Visit 2)
- Concurrent or previous use of drugs approved for weight loss (eg, orlistat, bupropion-naltrexone, phentermine-topiramate, phentermine, lorcaserin) and within the last 30 days or 5 half-lives of the drug, whichever is longest, prior to the start of the study (Visit 2)

- Concurrent use of aspirin (acetylsalicylic acid) at a dose greater than 150 mg once daily and within the last 72 hours prior to the start of the study (Visit 2)
- Concurrent use of paracetamol (acetaminophen) at a total daily dose greater than 3000 mg once daily and within the last 72 hours prior to the start of the study (Visit 2)
- Concurrent use of ascorbic acid (vitamin C) at a total daily dose of > 1000 mg and within the last 72 hours prior to the start of the study (Visit 2)
- Concurrent use of opiates, domperidone, metoclopramide, or other drugs [REDACTED] within 2 weeks prior to the start of the study (Visit 2) [REDACTED]
- Concurrent use of medications (other than metformin) for control of blood glucose within 4 weeks prior to the start of the study (Visit 2) unless it is deemed necessary by the investigator for safety reasons.

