5.4.1 Time Period for Collection of Adverse Events

All AEs will be collected from the time of admission to the clinical unit (Day -2 for Cohort 1 and Day -2 [REDACTED] for Cohort 2) throughout the treatment period and including the follow-up period (7 to 14 days after the last dose of investigational product; Visit 10 for Cohort 1 [Table 4.2.2-1] and Visit 8 [Table 4.2.2-2] for Cohort 2). Additionally, all SAEs will be collected from time of signature of informed consent throughout the treatment period and including the follow-up period as described above.

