5.4.2 Follow-up of Unresolved Adverse Events

Any AEs that are unresolved at the subject’s last visit in the study are followed up by the investigator for as long as medically indicated, but without further recording in the eCRF. MedImmune retains the right to request additional information for any subject with ongoing AE(s)/SAE(s) at the end of the study, if judged necessary. Updates regarding SAEs that were ongoing at the time of the subject’s completion of study participation should be submitted to the study representative using a paper SAE follow-up form.

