6.3 Study Timetable and End of Study

An individual subject will be considered to have completed the study if the subject was followed through the last protocol-specified visit/assessment, regardless of the number of doses of investigational product that was received.

Subjects will be considered not to have completed the study if consent was withdrawn or the subject was lost to follow-up (Sections 4.1.5 and 4.1.6).

The end of the study (“study completion”) is defined as the date of the last protocol-specified visit/assessment for the last subject in the study.

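### Section 4.1.6 lets follow-up end when a subject off product starts an undefined alternative treatment; this conflicts with the safety schedule and can leave co-primary values to LOCF

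*Protocol*

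**What the plan says.** The default in Protocol section 4.1.6 is sound: "Subjects who are permanently discontinued from receiving investigational product will be followed for protocol-specified assessments including follow-up of any AEs unless consent is withdrawn" from study participation. The same sentence then adds three more ways for follow-up to end: "the subject is lost to follow-up, the subject starts alternative treatment, or the subject is enrolled in another clinical study". The protocol does not define alternative treatment.

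Other sections bear on the same subjects:

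- Section 5.4.1 collects all AEs through a follow-up visit placed "7 to 14 days after the last dose of investigational product", and "all SAEs will be collected from time of signature of informed consent throughout the treatment period" and that same follow-up period.
- Table 4.2.3-1 schedules a final visit 28 days (± 3) after last dose with AE/SAE assessment, ADA, laboratory tests, HbA1c, weight, ECG and, in Cohort 1, ABPM.
- Section 4.2.3.1 describes one visit for subjects who leave the study early. It includes weight, ECG, vital signs, chemistry and haematology, PK, ADA and AEs, but no MMTT, HbA1c or ABPM.
- Section 5.4.2 leaves AEs unresolved at the last visit with the "investigator for as long as medically indicated, but without further recording in the eCRF".
- Section 6.3 on completion status: "Subjects will be considered not to have completed the study if consent was withdrawn or the subject was lost to follow-up".
- SAP section 3.1 applies LOCF to efficacy endpoints. SAP section 3.2 keeps every dosed subject in the ITT population.

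**The concern.** Withdrawn consent and loss to follow-up make further data unobtainable. Starting another treatment does not: the subject still consents and can attend. Ending follow-up at that point is a choice to stop collecting, and it is triggered after randomisation by something that may reflect poor tolerability or poor glycaemic control. The missing data may therefore be unbalanced between arms and related to outcome.

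Two things are at stake. One is the secondary safety objective, which covers dosing and follow-up: late AEs, AE resolution, the post-treatment ADA sample and the final ABPM. The other is the co-primary analysis in Cohort 1, where a released subject has no Day 49 MMTT or Day 50 weight and an earlier value is carried forward.

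**Working it through.** The plan states no figure on this point, so there is none to reproduce. The check is a comparison of the sections, followed by simple arithmetic for scale.

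**1. Does the exception appear elsewhere?**

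| Provision | Data after product is stopped | Alternative-treatment exception? |
|---|---|---|
| 4.1.6 | Protocol assessments and AE follow-up | Yes |
| 5.4.1 | AEs and SAEs to 7-14 days after last dose | No |
| Table 4.2.3-1 | Safety, ADA and (Cohort 1) ABPM at 28 days | No |
| 4.2.3.1 | One exit visit, if release counts as leaving the study | No |
| 5.4.2 | Unresolved AEs, outside the eCRF | No |
| 10.5 and 5.6.3.1 | Potential Hy's Law cases; pregnancy outcome | No |

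No section says which provision prevails, so two sites could treat the same subject differently and each point to the protocol.

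**2. How much AE collection can be lost in one subject?** Take a Cohort 1 subject with last dose on Day 10 who starts another treatment on Day 12 (illustrative days).

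- Under 5.4.1, collection would run to between Day 10 + 7 = Day 17 and Day 10 + 14 = Day 24. Loss: 17 − 12 = 5 days to 24 − 12 = 12 days.
- If the 28-day visit governs, it would run to Day 10 + 28 = Day 38 (± 3). Loss: 38 − 12 = 26 days.

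The gap between 12 and 26 arises because 5.4.1 and Table 4.2.3-1 differ on when AE assessment ends, which also needs reconciling.

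**3. What happens to the co-primary endpoints?** Cohort 1 has plasma-sampled MMTTs on Days −1, 7 and 49 only. The subject in step 2 has a Day 7 test, taken at 50 µg, and no later one, because the exit visit has no MMTT. LOCF then supplies the Day 7 AUC as the Day 49 result. For weight, LOCF takes the last recorded value, which may be the exit-visit weight if that visit is held. The direction of the resulting error cannot be determined from the documents.

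**4. How many subjects?** The documents give no rate of stopping or of starting other treatment. As an assumption, let 5-20% of active subjects stop early and half of those start another treatment.

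- Both cohorts: 0.05 × 44 × 0.5 = 1.1 to 0.20 × 44 × 0.5 = 4.4, about 1-4 subjects. One unrecorded AE moves the active-arm incidence by 1/44 = 2.3 percentage points.
- Cohort 1, where the co-primary endpoints are analysed: 0.05 × 26 × 0.5 = 0.65 to 0.20 × 26 × 0.5 = 2.6, about 1-3 subjects.

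**5. Effect on seeing a late event.** With an assumed per-subject late-event risk p and k active subjects no longer observed, P(at least one event) = 1 − (1 − p)^(44 − k).

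| p | k = 0 | k = 4 | k = 6 |
|---|---|---|---|
| 2% | 58.9% | 55.4% | 53.6% |
| 5% | 89.5% | 87.1% | 85.8% |
| 10% | 99.0% | 98.5% | 98.2% |

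This assumes that risk is unrelated to release. If released subjects are at higher risk, the loss is larger.

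**The case against.** The strongest reply is that 4.1.6 must be read with the rest of the protocol. The exit visit in 4.2.3.1 would give one last weight, ECG, laboratory, ADA and AE assessment; unresolved AEs stay with the investigator; potential Hy's Law cases and pregnancies are followed regardless. That stands. A reader might infer from 4.1.6 alone that all AE follow-up stops, and the documents do not support that. What remains is thinner than the schedule, however: the exit visit is a single visit, it applies only if release is read as leaving the study, and follow-up under 5.4.2 does not reach the database.

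It can also be said that a specific rule in 4.1.6 overrides the general windows. That would settle the conflict but leave the loss of data in place.

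Other stronger readings also fail:

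- A reader might infer that released subjects are those most likely to have an adverse outcome. This is plausible, but no statement or rate in the documents shows it.
- A reader might see a contradiction with section 6.3. That section does not say its list is exhaustive, and it cross-refers to 4.1.6. There is a classification gap: a released subject is neither followed to the last visit nor a listed non-completer.
- A reader might see a contradiction with section 4.7.2, which bars new glucose-lowering drugs in the dosing and follow-up period "unless it is deemed necessary by the investigator for safety and following discussion with the medical monitor". It says nothing about ending or keeping follow-up, and the exception in 4.1.6 reaches only subjects already off product. If anything, 4.7.2 limits how often the exception would be triggered.

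Finally, the numbers are small. With four subjects cut off and a 5% risk, the chance of seeing a late event falls only from 89.5% to 87.1%. That is fair for event detection, but it does not address the carried-forward co-primary value.

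**Conclusion.** The point holds as a conflict between sections and an avoidable loss of data. Section 4.1.6 permits assessments and AE follow-up to end on an undefined trigger that 5.4.1 and Table 4.2.3-1 do not recognise. Safety follow-up is reduced, not eliminated.

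The size is modest: about 1-4 active subjects under the assumed rates, and 5-12 days of AE collection (26 if the 28-day visit governs) in the illustrated subject. The more consequential effect is in Cohort 1, where a 50 µg AUC from Day 7 can stand for the Day 49 result in an arm of 26. This rests on reading the assessments promised by 4.1.6 as including the Day 49 and Day 50 visits for subjects off product. Whether release would differ by arm is a reasonable worry, not a documented fact. This is a cheap improvement rather than a threat to the trial.

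**What to change.** Delete the alternative-treatment exception from section 4.1.6. Record the type and start date of any such treatment in the eCRF. Continue the scheduled safety, ADA and co-primary assessments unless consent is withdrawn or the subject is lost to follow-up. Reconcile 4.1.6 with 5.4.1, 4.2.3.1, Table 4.2.3-1 and the completion definitions in 6.3, including which visit ends AE collection. If the exception is kept, define the term and exempt the safety, ADA and co-primary visits from it.

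The change concerns data collection only and leaves every treatment decision as it is. The cost is a short amendment, since the visits are already scheduled for every subject. The downside is that some data will be collected under other treatment and must be flagged in the analysis and listings.

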4.1.7 Replacement of Subjects

Subjects who withdraw from the study will be replaced where possible. A maximum number of five subjects may be replaced in each cohort.

4.1.8 Withdrawal of Informed Consent for Data and Biological Samples

Biological Samples Obtained for the Main Study

Study data are protected by the use of an SID number, which is a number specific to the subject. The investigator is in control of the information that is needed to connect a study sample to a subject. A subject's consent to the use of data does not have a specific expiration date, but the subject may withdraw consent at any time by notifying the investigator. If consent is withdrawn, any samples collected prior to that time may still be given to and used by the sponsor but no new data or samples will be collected unless specifically required to monitor safety of the subject.

If a subject withdraws consent to the use of donated biological samples, the samples will be disposed of/destroyed, and the action documented. If samples are already analysed, MedImmune is not obliged to destroy the results of this research.

[REDACTED]

[REDACTED]

[REDACTED]

[REDACTED]

[REDACTED]

[REDACTED]

4.2 Schedule of Study Procedures

4.2.1 Enrollment/Screening Period

Table 4.2.1-1 shows all procedures to be conducted at the screening visit. Assessments should be performed in the order shown in the table.

Whenever vital signs, 12-lead ECGs, and blood draws are scheduled for the same nominal time, the assessments should occur in the following order: 12-lead ECG, vital signs, and then blood draws. The timing of the first 2 assessments should be such that it allows the blood draw (eg, MMTT blood sample) to occur at the exact nominal time.

Table 4.2.1-1 Schedule of Screening Procedures

Study Period	Screening
Visit Number	V1
Procedure/Study Day	Day -60 to Day -2
Written informed consent/assignment of SID number	X
[REDACTED]	■
[REDACTED]	■

Table 4.2.1-1 Schedule of Screening Procedures

Study Period	Screening
Visit Number	V1
Procedure/Study Day	Day -60 to Day -2
Medical history, including smoking and alcohol history	X
Physical examination (full) including structured neurological examination ^a	X
Verify eligibility criteria	X
Weight, height, and BMI calculation	X
Demographics	X
12-lead ECG ^b	X
Vital signs (BP ^c , heart rate, body temperature, RR)	X
Collect blood for:	
LFTs, CR, and eGFR calculation only	X
Haematology (FBC)	X
HbA1c	X
Calcitonin	X
HIV-1 and -2 antibodies; hepatitis B and C serology	X
Collect urine for:	
Urinalysis	X
Drug and alcohol screen	X
Urine or serum pregnancy test if applicable	X
CGM device demonstration ^d	X
SC injection self-administration training ^e	X
Concomitant medications	X

BMI = body mass index; BP = blood pressure; CGM = continuous glucose monitoring; CR = creatinine; ECG = electrocardiogram; eGFR = estimated glomerular filtration rate; FBC = full blood count; HbA1c = glycated haemoglobin; HIV = human immunodeficiency virus; LFTs = liver function tests (albumin; alanine transaminase [ALT], aspartate transaminase [AST], alkaline phosphatase [ALP], and total bilirubin); RR = respiration rate; SC = subcutaneous; SID = subject identification; V = visit

^a examination is required.

^b A single digital ECG recording should be performed after the subject has rested in the supine position for 10 minutes.

^c Blood pressure should be measured once at heart level in the nondominant arm where possible, after the subject has rested in either a seated or supine position for at least 10 minutes.

^d Cohort 1 only; subjects should be shown the device and given an explanation as to how it is worn; allocation to Cohort 2 may be preferable for subjects who would rather not use a CGM device during the study.

^e Subject's ability to self-administer investigational product will be verified using normal saline subcutaneous injections.

4.2.2 Randomised Treatment Period

Table 4.2.2-1 and Table 4.2.2-2 show all procedures to be conducted during the treatment period for Cohort 1 and Cohort 2, respectively. Assessments should be performed in the order shown in the table.

Whenever vital signs, 12-lead ECGs, and blood draws are scheduled for the same nominal time, the assessments should occur in the following order: 12-lead ECG, vital signs, and then blood draws. The timing of the first 2 assessments should be such that it allows the blood draw (eg, PK blood sample) to occur at the exact nominal time. Subjects are expected to fast overnight with water permitted only for all study visits.

Table 4.2.2-1 Schedule of Treatment Period Study Procedures: Cohort 1

Study Period	Inpatient		Inpatient or daily visits	Outpatient		Inpatient		Outpatient		Inpatient		Outpatient							
	-2	-1		1	2-6	7	15	22	23	29	36	43	49	50					
Study Day																		7 to 14 Days Post Last Dose	
Visit Number																			V10
Procedure																			
Verify eligibility criteria ^a																			
Admit to clinical unit ^b	X											X							
Discharge from clinical unit ^c													X						X
Outpatient visit to clinic ^c			(X)	(X)						X	X			X	X				X
Medical and disease history	X																		
Pregnancy test (if applicable) ^d	X									X									
Targeted physical examination	X									X		X		X	X				
Vital signs (BP, heart rate, body temperature, RR) ^e	X		X							X		X	X	X	X				X
ABPM ^f	X											X		X	X				
ECG ^g										X		X		X	X				X
Body weight ^h										X		X		X	X				X
SC injection training using normal saline	X	X	X																
Randomisation ⁱ			X																
Subjects required to fast overnight for 10 hours ^j	X	X		X(D6)								X(D21)						X(D48 & 49)	
IP administration ^k (SC)			X	X						X	X	X		X	X				
Up-titration ^l					X	X				X	X	X							

Table 4.2.2-1 Schedule of Treatment Period Study Procedures: Cohort 1

Study Period	Inpatient		Inpatient or daily visits	Outpatient		Inpatient		Outpatient		Inpatient		Outpatient		
	-2	-1		1	2-6	7	15	22	23	29	36	43	49	50
Study Day														
Visit Number	V2		V3	V4	V5	V6	V7	V8	V9	V10				
Collect blood for:														
Haematology panel (predose as applicable) ^m	X (Day -7 to -3)		X		X	X	X	X	X	X	X	X	X	X
Serum chemistry panel (predose as applicable) ^m	X (Day -7 to -3)		X		X	X	X	X	X	X	X	X	X	X
Lipase and amylase			X					X				X		
Calcitonin											X			
Fasting lipid profile		X			X						X			
Fasting HbA1c		X			X						X			
PK for MEDI0382 ⁿ		X			X	X	X	X	X	X	X	X	X	X
ADA ^o			X						X					
[REDACTED]														
[REDACTED]														
Capillary blood ketone and beta hydroxybutyrate ^q		X			X							X		
Free fatty acids (predose)		X										X		
[REDACTED]														

Table 4.2.2-1 Schedule of Treatment Period Study Procedures: Cohort 1

Study Period	Inpatient		Inpatient or daily visits	Outpatient			Inpatient		Outpatient			Outpatient 7 to 14 Days Post Last Dose
	-2	-1		1	2-6	7	15	22	23	29	36	
Visit Number	V2			V3	V4	V5	V6	V7	V8	V9	V10	
[REDACTED]					■							
Fasting amino acids (predose)		X								X		
[REDACTED]		■								■		
Fasting uric acid		X								X		
[REDACTED]		■								■		
MMTT Type B - blood samples for glucose only ¹					X							
Collect urine for:												
Urinalysis (dipstick; predose as applicable)		X			X							X
Drug and alcohol screen	X											
MMTT Type C (no blood sampling) ^s		X										X
CGM device training	X	X	X									
CGM ^t	←	-----To be worn continuously throughout until Day 50-----→										
CGM sensor application/change ^u	X				X			X			X	
Glucometer and diary provision ^v	←	-----Subjects will be expected to check capillary blood glucose levels if they are unwell or have symptoms of hypoglycaemia-----→										
AEs/SAEs	←	-----For the duration of the study-----→										
Concomitant medications	←	-----For the duration of the study-----→										

Table 4.2.2-1 Schedule of Treatment Period Study Procedures: Cohort 1

Study Period	Inpatient		Inpatient or daily visits		Outpatient		Inpatient		Outpatient		Inpatient		Outpatient	
	-2	-1	1	2-6	7	15	22	23	29	36	43	49	50	7 to 14 Days Post Last Dose
Study Day														
Visit Number	V2		V3	V4	V5	V6	V7	V8	V9	V10				

ADA = anti-drug antibody; AE = adverse event; APBM = ambulatory blood pressure monitoring; BP = blood pressure; CGM = continuous glucose monitoring; D = day; ECG = electrocardiogram; GLP-1 = glucagon-like peptide-1; HbA1c = glycated haemoglobin; IP = investigational product; min = minutes; MMTT = mixed-meal tolerance test; PD = pharmacodynamic(s); PK = pharmacokinetic(s); RR = respiration rate; SAE = serious adverse event; SC = subcutaneous; V = Visit.

Note: Whenever vital signs, ECGs, and blood draws are scheduled for the same nominal time, the ECG should occur first, then vital signs, and blood draws should occur last. The timing of the ECGs and/or vital signs should be such that it allows the blood draw (eg, for PK and PD) to occur as close as possible to the scheduled time. Ten minutes of supine rest should precede these assessments.

- a The eligibility check should be based on all clinical measurements and blood tests taken during the screening visit (V1) with the exception of eGFR, liver function tests, blood pressure, urinary illicit drug, alcohol and pregnancy tests, which should be rechecked on Day -2. A targeted physical examination and repeat medical history should also be undertaken to ensure the subject is well enough to commence dosing.
- b The diet of subjects should not be restricted in any way during the study (including during inpatient stay) unless fasting or a standardised meal is specified.
- c Subjects who prefer to attend for daily visits during the first week will be discharged home on Day 1 after all assessments are complete. (X) indicates that subjects can be inpatients or outpatients at these visits.
- d A serum or urine pregnancy test should be conducted on any female subject of childbearing potential as detailed in the schedule. Pregnancy tests do not need to be conducted in women who are surgically sterile (ie, bilateral tubal ligation, bilateral oophorectomy, or complete hysterectomy) or are postmenopausal (defined as at least 1 year since last menses and having an elevated follicle stimulating hormone laboratory value which is in the postmenopausal range in previous laboratory test results).
- e Vital Signs Schedule (blood pressure, heart rate, respiratory rate, and temperature): on days where ABPM is due to be checked a predose set of vital signs should be performed prior to application of the ABPM cuff. Blood pressure should be measured once at heart level in the nondominant arm where possible, opposite to the arm where the CGM device is applied, after the subject has rested in either a seated or supine position for at least 10 minutes. For time points where ECG recording precedes vital sign measurement, the 10-minute rest in the supine position prior to the ECG suffices for the rest prior to vital sign measurement.
 - o Day -2; vital signs to be taken prior to fitting the ABPM device; postural (standing and supine) blood pressures should be performed at this time.
 - o Day 1; vital signs to be taken; predose (-15 min), 15, 30, and 60 minutes (\pm 5 min) and 2 hours (\pm 10 min) postdose

- o Day 7, 15; 23 no specific time point
 - o Day 22, 29, 36, and 43; vital signs to be taken prior to fitting ABPM device
 - o Day 49: vital signs to be taken prior to fitting the ABPM device; postural (standing and supine) blood pressures should be performed at this time.
- f Subjects will be fitted with the ABPM device while at the clinical unit, which may involve practice inflations. The ABPM device should be applied on the opposite arm to the arm where the CGM device is applied. The subject will then wear the monitor/cuff for approximately 24 hours (including overnight at home) and will remove the device at home at the end of the 24-hour period. Subjects will return the device to the clinic.
- g A single digital ECG recording should be performed predose after the subject has rested for 10 minutes in the supine position on Day 1, 7, 22, and 49. No specific time point for other visits.
- h Body weight should be measured in the morning prior to breakfast (predose on Day 1); the subject should take off their shoes and remove bulky clothing. Calibrated scales should be used.
- i Randomisation may occur any time from Day -1 to Day 1 predosing.
- j Subjects are required to fast overnight on the night of Day -2, -1, 6, 21, 48, and 49. Refer to footnote (s) for additional fasting requirements on Day -2 and Day 49 during the day.
- k Subjects are required to dose at the clinic on Day 1 – 7 as dilution of dose is required by site staff. Subjects are also required to dose at the clinic on study day visits when predose assessments are required. See Section 4.5.1.3 for further information.
- l On Day 7, the subject will receive a final 50-µg dose, and should be provided with 7 days of IP supply to dose at the 100-µg dose level and advised to commence this dose level on Day 8 while they are at home. On Day 15, subjects will be given a 200-µg dose during their study visit, and should be provided with 6 days IP supply for dosing at the 200-µg dose level while at home. Subjects should be given the first 300-µg dose on Day 22 and continue this dose level for the remainder of the study.
- m Predose not applicable on Days 7, 29, 36, and 43. An additional blood test for safety (to be taken at any time between Day -3 and Day -7) is not required if the screening visit occurs within 7 days of dosing (Day 1); if the screening visit is more than 7 days prior to dosing on Day 1, then additional safety blood tests should be taken (as described in Section 4.3.3).
- n PK Sampling Schedule for MED10382:
Day -1; No specific time point
Day 1; Predose
Day 7 and Day 15; Predose
Day 22; Predose, 1, 2 (± 15 min); 4, 6, 8, and 12 (± 30 min) hours postdose
Day 23: Predose
Day 29; 36; 43 Predose
Day 49; Predose, 1, 2 (± 15 min); 4, 6, 8, and 12 (± 30 min) hours postdose
Day 50; Predose

^o ADA Sampling Schedule: Day 1 predose; Day 29 predose; Day 50 predose; and 28 days after administration of the last dose in the study

■ [REDACTED]

^q Capillary blood ketone (point-of-care testing) and serum beta-hydroxybutyrate will be measured at baseline after at least 10 hours fasting on Day -1 and predose and 4 hours postdose on Day 22, and Day 49 with fasting for at least 10 hours the night before.

^r MMTT Type A and B Schedule: Following a minimum 10-hour fast overnight and 2.5 hours after taking the IP, a blood sample for glucose (Type B) or glucose metabolism panel [REDACTED] will be taken immediately prior (within 15 minutes) to the subject drinking one entire can of Ensure Plus as a standardised meal (ie, “0 minutes”). Blood samples for glucose metabolism panel will additionally be drawn at 15, 30, 45, 60, 90, 120, 180, and 240 minutes (\pm 5 min) after consumption of the standardised meal.

^s MMTT Type C Schedule: the subject should be fasted from 1400 hours (\pm 15 min) and receive water only from this time until 2000 hours. A standardised liquid meal (one entire can of Ensure Plus) should be administered to the subject at 1800 hours. The subject should ensure that they are wearing their CGM device before, during, and after the test. No additional blood tests are required to be taken during this period, and the subject will be permitted to eat and drink freely from 2000 hours onwards.

^t CGM device should be worn continuously throughout the study and the sensor should be applied to the arm, taking into account subject preference and which side the ABPM device will be used on. The sensor applied to the skin is single-use and may not be re-attached once removed.

^u CGM sensor application should occur at approximately 1200 hours on Day -2; thereafter, existing CGM sensors should be removed and a new sensor applied at 1200 hours \pm 20 minutes on Days 7 and at any time on Day 36. On Day 22, the old sensor should be removed and a new sensor applied predose and ideally should be the first study procedure performed at that visit. If the sensor fails, or needs to be replaced, it should be re-applied as soon as possible. The CGM sensor should be removed after 0800 hours on Day 50. Whenever a new CGM sensor is applied, at least 1 hour afterwards, the site staff should place the monitor in close proximity with the sensor to transfer data and ensure that the sensor and monitor are functioning adequately.

^v A glucometer, test strips, and a diary should be provided to the subject. The subject should be trained in its use and advised to test their capillary blood glucose at any time the subject feels unwell or has symptoms of hypoglycaemia (hunger, dizziness, shaking, sweating, or irritability).

Table 4.2.2-2 Schedule of Treatment Period Study Procedures: Cohort 2

Study Period	Inpatient		Inpatient or daily visits	Inpatient		Inpatient or daily visits	Inpatient		Inpatient or daily visits	Outpatient		Outpatient	
	-2	-1		1	2-6		7	8		9-13	14		15
Visit Number	V2		V3		V4		V5		V6		V7		V8
Procedure													
Verify eligibility criteria ^a		X											
Admit to clinical unit ^b	X				X							X	
Discharge from clinical unit ^c				(X) (D2)		(X)			X				X
Outpatient visit to clinic ^c				(X)						X			X
Medical and disease history	X												
Pregnancy test (if applicable) ^d	X								X			X	
Targeted physical examination	X				X				X		X	X	
Vital signs (BP, heart rate, body temperature, RR) ^e	X		X		X	X		X	X	X	X	X	X
ECG ^f			X		X				X		X	X	
Body weight ^g			X								X	X	
SC injection training	X	X	X										
Randomisation ^h		X											
Subject required to fast overnight for 10 hours ⁱ	X (D-3 and D-2)	X		X (D6)			X (D13)	X		X (D28)	X (D42)	X (D48 and D49)	
IP administration ^j			X	X	X	X							
Up-titration ^k									X	X	X		
Collect blood for:									X	X	X		

Table 4.2.2-2 Schedule of Treatment Period Study Procedures: Cohort 2

Study Period	Inpatient		Inpatient or daily visits		Inpatient		Inpatient or daily visits		Inpatient		Outpatient		Inpatient		Outpatient	
	-2	-1	1	2-6	7	8	9-13	14	15	29	43	49	50	7 to 14 Days Post Last Dose		
Study Day																
Haematology panel (predose as applicable) ¹	X (Day -7 to -3)	X	X		X				X	X		X			X	
Serum chemistry panel (predose as applicable) ¹	X (Day -7 to -3)	X	X		X				X	X		X			X	
Lipase and amylase					X				X			X				
Fasting lipid profile					X				X			X				
Calcitonin																
HbA1c		X			X				X			X				
PK for MEDI0382 ^m		X	X	X (D2)	X	X			X	X	X	X	X			
MMTT Type B :blood samples for glucose only ⁿ					X				X							
ADA ^o		X														

Table 4.2.2-2 Schedule of Treatment Period Study Procedures: Cohort 2

Study Period	Inpatient		Inpatient or daily visits		Inpatient or daily visits		Inpatient		Outpatient		Outpatient		
	-2	-1	1	2-6	7	8	9-13	14	15	29	43	49	50
Study Day													
Collect urine for;													
Urinalysis (dipstick; predose as applicable)	X		X					X				X	
Drug and alcohol screen	X												
[REDACTED]													
[REDACTED]													
Glucometer and diary provision and capillary blood glucose monitoring ^s	←---Subjects will only be expected to check capillary blood glucose levels if they are unwell or have symptoms of hypoglycaemia--->												
AEs/SAEs	←-----For the duration of the study----->												
Concomitant medications	←-----For the duration of the study----->												

ADA = anti-drug antibody; AE = adverse event; BP = blood pressure; CGM = continuous glucose monitoring; D = day; ECG = electrocardiogram; eCRF = electronic case report form; [REDACTED] GLP-1 = glucagon-like peptide-1; HbA1c = glycated haemoglobin; IP = investigational product; LFT = liver function tests; min = minutes; MMIT = mixed-meal tolerance test; PD = pharmacodynamic(s); PK = pharmacokinetic(s); RR = respiration rate; SAE = serious adverse event; SC = subcutaneous; V = Visit

Note: Whenever vital signs, ECGs, and blood draws are scheduled for the same nominal time, the ECG should occur first, then vital signs, and blood draws should occur last. The timing of the ECGs and/or vital signs should be such that it allows the blood draw (eg, for PK and PD) to occur as close as possible to the scheduled time. Ten minutes of supine rest should precede these assessments.

- ^a The eligibility check should be based on all clinical measurements and blood tests taken during the screening visit (V1) with the exception of eGFR, liver function tests, blood pressure, urinary illicit drug, alcohol and pregnancy tests, which should be rechecked on Day -2. A targeted physical examination and repeat medical history should also be undertaken to ensure the subject is well enough to commence dosing.
- ^b The diet of subjects should not be restricted in any way during the study (including during inpatient stay) unless fasting or a standardised meal is specified.

-
- c Subjects who prefer to attend for daily visits will be discharged home on Day 2 and will be readmitted for overnight stays on Day 7 and Day 14.
- d A pregnancy test should be conducted on any female subject of childbearing potential as detailed in the schedule. Pregnancy tests do not need to be conducted in women who are surgically sterile (ie, bilateral tubal ligation, bilateral oophorectomy, or complete hysterectomy) or are postmenopausal (defined as at least 1 year since last menses and having an elevated follicle stimulating hormone laboratory value which is in the postmenopausal range in previous laboratory test results).
- e Vital Signs Schedule (blood pressure, heart rate, respiratory rate, and temperature): On Days 1, 7, and 14 vital signs are to be recorded predose (-15 min) and at 15, 30, 60, 90 (\pm 5 min) minutes and 2 hours postdose (\pm 10 min), and predose (-15 min) at all other times. Vital signs should be performed after the subject has rested in either a seated or supine position for at least 10 minutes prior to the measurement. For time points where ECG recording precedes vital sign measurement, the 10-minute rest in the supine position prior to the ECG suffices for the rest prior to vital sign measurement.
- f A single digital ECG recording should be performed predose after the subject has rested in the supine position for 10 minutes.
- g Body weight should be measured in the morning prior to breakfast (predose on Day 1); the subject should take off their shoes and remove bulky clothing. Calibrated scales should be used.
- h Randomisation may occur on either Day -1 to Day 1 predosing.
- i Subjects are required to fast overnight on the night of Day -3 [REDACTED] -2, -1, 6, 13, 14, 28, 42, 48, and 49.
